## VERSION HISTORY

This Statistical Analysis Plan (SAP) for study SAR442720 TCD16210 is based on the protocol dated 26-Oct-2021. This section summarizes major changes to the statistical analysis features in the SAP. This SAP is approved before database lock of the expansion cohort.

**Table 1 - Major changes in statistical analysis plan**

SAP Version	Approval Date	Changes	Rationale
1.0		This is the original version of SAR442720 TCD16210 SAP.	

## 1 INTRODUCTION

### 1.1 STUDY DESIGN

#### Part-1

This is a Phase 1 open-label, multi-center, safety, preliminary efficacy, and PK study of SAR442720 in combination with pembrolizumab in participants with advanced malignancies.

The Phase 1 safety study is to characterize the safety and tolerability of SAR442720 in combination with pembrolizumab and to confirm the recommended Phase 2 dose (RP2D). Participants with either NSCLC or advanced CRC will be enrolled in the study. There is no minimum patient number requirement for either tumor type.

There are 3 scheduled dose levels in the consideration: the starting dose (DL 1) of SAR442720 (140 mg BIW), dose level 2 (DL2) (200 mg BIW) and DL-1 (100 mg BIW). The DLT observation period is 1 cycle (21 days). The Study Committee will review the overall safety, PK/PD and preliminary antitumor activity data and will decide the recommended dose for the expansion phase.

#### Part-2

The expansion cohort (Part-2), un-controlled, non-randomized, open-label study will assess the antitumor activity and safety of SAR442720 combined with pembrolizumab in participants with lung cancer.

Part-2 will assess the antitumor efficacy and safety of adding SAR442720 to therapeutic approaches with documented efficacy profile as 1L NSCLC therapy.

- Cohort A1: participants with PD-L1 TPS  $\geq 50\%$  NSCLC to receive SAR442720 + pembrolizumab as 1L therapy.
- Cohort A2: participants with PD-L1 TPS 1%-49% NSCLC to receive SAR442720 + pembrolizumab as 1L therapy.

Part-2 of the study will start at the RP2D for SAR442720 defined in Part-1. The SAR442720 RP2D will be 200 mg BIW, such Day 1 and Day 2 of each week, administered orally (21 days per cycle). Pembrolizumab will be administrated as a dose of 200 mg using 30 minutes IV infusion on Day 1 every 3 weeks (21 days cycle) or a dose of 400 mg using 30 minutes IV infusion on Day 1 every 6 weeks (42 days cycle).

#### Part-3

Part-3 of this open-label, multi-center, un-controlled, non-randomized study, will assess the safety, RP2D, anti-tumor activity, and PK of SAR442720 in combination with adagrasib in participants with NSCLC harboring KRAS G12C mutation.

Part-3A of the study will investigate the safety and tolerability of SAR442720 in combination with adagrasib and confirm RP2D. There are 6 dose levels in consideration: the starting dose (dose level 1 [DL1]) of IMP combination will be 100 mg BIW and 400 mg BID for SAR442720 and adagrasib respectively, dose level 2 (DL2) will be 140 mg BIW and 400 mg BID, dose level 3a (DL3a) will be 140 mg BIW and 600 mg BID, dose level 3b (DL3b) will be 200 mg BIW and 400 mg BID, dose level 4 (DL4) will be 200 mg BIW and 600 mg BID, and dose level (-1) ([DL-1]) will be 80 mg BIW and 400 BID. A minimum of 3 DLT evaluable participants for each dose level is required. The DLT observation period is 1 cycle (21 days). The Study Committee will review the overall safety, PK/PD, and clinical activity data and in agreement with the Sponsor's Study Medical Manager, will decide the recommended dose for the expansion phase.

Part-3B dose expansion will assess the anti-tumor activity and safety of SAR442720 combined with adagrasib in participant with NSCLC harboring KRAS G12C mutation. This study will start once RP2D for SAR442720 and adagrasib from Part-3A dose escalation is confirmed. Approximately 40 participants will be enrolled.

Part-4 of this study will assess the effect of food on PK of SAR442720 tablet, when dosed in combination with pembrolizumab in participants with advanced malignancies. It will also evaluate the relative bioavailability of SAR442720 tablet formulation (test) compared to the capsule formulation (reference) when dosed in combination with pembrolizumab. Approximately 12 participants are expected to be enrolled.

## 1.2 OBJECTIVE AND ENDPOINTS

**Table 2 - Objectives and endpoints**

### Part-1

	Objectives	Endpoints
Primary	

To characterize the safety and tolerability for the combination of SAR442720 and pembrolizumab in participants with advanced solid tumors including NSCLC who progressed on anti-PD1/PD-L1 containing therapy and advanced CRC after progression to all standard of care (SoC) therapy

To define the MTD and RP2D for the combination of SAR442720 and pembrolizumab in participants with solid tumors

	

Incidence, nature, and severity of treatment-emergent adverse events (AEs) and serious adverse events (SAEs), graded according to the National Cancer Institute Common Terminology Criteria for Adverse Events (NCI CTCAE) Version 5.0 for the combination of SAR442720 and pembrolizumab

Incidence of study drug-related dose limiting toxicities (DLTs) in Cycle 1

Secondary	

To document the pharmacokinetic (PK) for the combination of SAR442720 and pembrolizumab, and to document the PK of pembrolizumab in combination with SAR442720

To estimate the anti-tumor effects for the combination of SAR442720 and pembrolizumab in all participants

	

Plasma concentrations of SAR442720

Serum concentrations of pembrolizumab

Objective response rate (ORR) and duration of response (DoR) for the combination therapy of SAR442720 and pembrolizumab in all participants. ORR of combination therapy with SAR442720 and pembrolizumab will be based on Response Evaluation Criteria in Solid Tumors (RECIST) v1.1

## Part-2

	Objectives	Endpoints
Primary	
 
To determine the antitumor activity of SAR442720 in combination with pembrolizumab
 
	
 
Objective response rate defined as the proportion of participants who have a confirmed complete response (CR) or partial response (PR) determined by investigator per RECIST v1.1
 

Secondary	
 
To assess the safety profile of SAR442720 in combination with pembrolizumab
 
To assess other indicators of antitumor activity
 
To assess the PK of SAR442720 in combination with pembrolizumab, and to assess the PK of pembrolizumab in combination with SAR442720
 
	
 
Incidence of TEAEs, SAEs, laboratory abnormalities according to National Cancer Institute Common Terminology Criteria for Adverse Events (NCI CTCAE) V5.0
 
Time to response (TTR) defined as the time from the first administration of investigational medicinal product (IMP) to the first documented evidence of PR or CR determined by investigator per RECIST v1.1 (for NSCLC)
 
DoR, defined as the time from first documented evidence of CR or PR until progressive disease (PD) determined by investigator per RECIST v1.1 or death from any cause, whichever occurs first
 
Clinical benefit rate (CBR) including confirmed CR or PR at any time or stable disease (SD) of at least 6 months determined by investigator per RECIST v1.1
 
Progression free survival (PFS), defined as the time from the date of first IMP administration to the date of the first documented disease progression determined by investigator as per RECIST v1.1 or death due to any cause, whichever occurs first
 
Plasma concentrations of SAR442720
 
Serum concentration of pembrolizumab
 

## Part-3A

	Objectives	Endpoints
Primary	
 
To define the MTD and RP2D for the combination of SAR442720 and adagrasib in participants with NSCLC and KRASG12C mutations
 
	
 
Incidence of study drug-related DLTs in Cycle 1
 

Secondary	
 
To characterize the safety and tolerability of SAR442720 in combination with adagrasib in participants with NSCLC and KRASG12C mutations
 
To characterize the PK of SAR442720 in combination with adagrasib, and to characterize the PK of adagrasib in combination with SAR442720
 
	
 
Incidence, nature, and severity of treatment emergent AEs and SAEs, graded according to the NCI CTCAE Version 5.0 for the combination of SAR442720 and adagrasib
 
PK parameters of SAR442720
 
PK parameters of adagrasib
 

Objectives	Endpoints

 
To estimate the anti-tumor effects of SAR442720 in combination with adagrasib in all participants
 
	
 
ORR and DoR of SAR442720 and adagrasib in all participants. ORR of combination therapy with SAR442720 and adagrasib will be based on RECIST v1.1
 

### Part-3B

	Objectives	Endpoints
Primary		
	
 
To determine the antitumor activity of SAR442720 in combination with adagrasib in participants with NSCLC and KRASG12C mutations
 
	
 
Objective response rate defined as the proportion of participants who have a confirmed CR or PR determined by investigator per RECIST v1.1
 

Secondary		
	
 
To assess the safety profile of SAR442720 when combined with adagrasib in participants with NSCLC and KRASG12C mutations
 
To assess other indicators of antitumor activity
 
	
 
Incidence of TEAEs, SAEs, laboratory abnormalities according to NCI CTCAE V5.0
 
TTR defined as the time from the first administration of investigational medicinal product (IMP) to the first documented evidence of PR or CR determined by investigator per RECIST 1.1 (for NSCLC)
 
DoR, defined as the time from first documented evidence of CR or PR until progressive disease (PD) determined by investigator per RECIST 1.1 or death from any cause, whichever occurs first
 
CBR including confirmed CR or PR at any time or SD of at least 6 months (determined by investigator per RECIST v1.1)
 
PFS, defined as the time from the date of first IMP administration to the date of the first documented disease progression determined by investigator as per RECIST v1.1 or death due to any cause, whichever occurs first
 
Plasma concentrations of SAR442720 and adagrasib
 

	
 
To assess the PK of SAR442720 in combination with adagrasib, and to assess the PK of adagrasib in combination with SAR442720
 
	

### Part-3 (Part-3A and Part-3B)

	Objectives	Endpoints
Tertiary/exploratory		
	[REDACTED]	[REDACTED]

**Part-4**

	Objectives	Endpoints
Primary	
 
• To evaluate the impact of food on the PK of SAR442720 when dosed in combination with pembrolizumab
 
• To evaluate the impact of formulation (tablets vs. capsules) on the PK of SAR442720 when dosed in combination with pembrolizumab
 
	
 
• Plasma PK parameters of SAR442720 following oral administration of SA442720 tablets in combination with pembrolizumab under fed and fasted states (eg. <math>C_{max}</math>, <math>T_{max}</math>, <math>AUC_{0-last}</math>)
 
• Plasma PK parameters of SAR442720 following oral administration of SAR442720 tablets (test formulation) and capsules (reference formulation) in combination with pembrolizumab under fasted state (eg. <math>C_{max}</math>, <math>T_{max}</math>, <math>AUC_{0-last}</math>)
 

Secondary	
 
• To assess the safety and tolerability of SAR442720 under fasted and fed conditions in combination with pembrolizumab, when dosing with capsule and tablet formulations in combination with pembrolizumab
 
• To estimate the anti-tumor effects of SAR442720 in combination with pembrolizumab in all participants
 
	
 
• Incidence, nature, and severity of treatment emergent AEs and SAEs, graded according to the NCI CTCAE Version 5.0 for SAR442720 in combination with pembrolizumab
 
• ORR and DoR of SAR442720 and pembrolizumab in all participants. ORR of combination therapy with SAR442720 and pembrolizumab will be based on RECIST v1.1
 

## 2 SAMPLE SIZE DETERMINATION

The sample size is not calculated from statistical consideration since there will not be any formal statistical test performed. Overall, up to 134 participants will be enrolled.

In Part-1, at least 6 patients need to be treated at the MTD. After MTD is identified, another 6 patients will be treated at the MTD to confirm the decision and determine the RP2D. Therefore, a range of 18-24 DLT-evaluable (defined in [Section 3](#)) patients will be enrolled in the Part-1 of this study. The actual sample size will vary depending on DLTs observed and the number of dose levels explored.

In Part-2, 40 participants, including 20 patients in Cohort A1 with PD-L1 TPS $\geq$ 50% and 20 patients in Cohort A2 with PD-L1 TPS in 1-49%, will be enrolled at the RP2D identified from the Part-1. With a sample size of 20 study participants in each cohort of Part-2, the probability of observing 1 or more instances of a specific AE with a true incidence rate of 1%, 2%, or 5% is 18.2%, 33.2%, or 64.2%, respectively.

Part-3A, a range of 15 to 30 DLT-evaluable participants will be enrolled in this study. The actual sample size will vary depending on DLTs observed and the number of dose levels explored.

Part-3B, 40 participants will be enrolled at the RP2D identified from the Part-3A. With a sample size of 40 study participants in each cohort of Part-3B, the probability of observing 1 or more instances of a specific AE with a true incidence rate of 1%, 2%, or 5% is 33.1%, 55.4%, or 87.1%, respectively.

Part 4, 12 participants are expected to be enrolled in each group. By assuming AUC single dose Coefficient of Variation is [REDACTED], 12 participants in each group will achieve a maximum imprecision of [REDACTED]. When the AUC ratio is [REDACTED], the 90% CI would be [REDACTED] [REDACTED] respectively. When 9 participants are PK evaluable in each group, the maximum imprecision would be [REDACTED]. When the AUC ratio is [REDACTED], the 90% CI would be [REDACTED] [REDACTED] respectively.

### 3 ANALYSIS POPULATIONS

The following populations for analyses are defined:

**Table 3 - Populations for analyses**

Population	Description
Enrolled	All participants who sign the ICF and have dose allocated to an intervention regardless of whether the intervention was received or not.
DLT-evaluable (only for Part-1 and Part-3A)	
Patients who take at least 4 of the 6 planned doses of SAR442720 (Part-1 and Part-3A) and 28 of the 42 planned doses of adagrasib (Part-3A) in the first cycle of the treatment and complete the DLT observation period.
 
OR
 
Patients who have any DLT observed in the DLT observation period.

PK	Patients who have at least one measurable SAR442720 concentration or at least one measurable pembrolizumab concentration after the first dose or at least one measurable adagrasib concentration after the first dose.
PD	Patients who have at least one PD marker result after the first dose
Safety	Patients who take at least one dose of any IMP (i.e., SAR442720, pembrolizumab, or adagrasib)
PK evaluable (Part-4 only)	Patients who complete all of cycle 1 and C2D1 with meal information, full PK, and no dose reduction/missed doses on C1D1, C1D15 and C2D1. Missing some PK samples may still be considered as evaluable and will be assessed case-by-cased.

Abbreviations: DLT = dose-limiting toxicity, ICF = informed consent form, PD = pharmacodynamic(s), PK = pharmacokinetic(s)

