E 22. Medication and supplements that may interfere or potentiate with SAR442720 and/or adagrasib metabolism or toxicity PRIOR or DURING study intervention are excluded:

- Strong CYP3A4 inducers or inhibitors (within 7 days prior)
- Strong P-glycoprotein (P-gp) inhibitors (eg, cyclosporine, tacrolimus; within 7 days prior)
- Strong Breast Cancer Resistance Protein (BCRP) inhibitors (eg, eltrombopag; within 7 days prior) (applies to Part-3 only)
- Proton pump inhibitors (within 3 days prior) or H2-receptor antagonists (within 1 day prior) during the dose escalation portion of the study
- Medications known to prolong QTc interval
- Acetylsalicylic acid (low dose aspirin, anticoagulation with low-molecular weight heparin or direct Factor X inhibitors and LMWH are allowed. Prophylactic LMWH is also allowed for high risk patients with hypercoagulability).

Diagnostic assessments

E 23. Inadequate organ and bone marrow function at the Screening visit:

- Absolute neutrophil count (ANC) $<1000 \mu\text{L} (1 \times 10^9/\text{L})$.
- Platelets $<100 \times 10^3 \mu\text{L}$ (after at least 3 days without platelet transfusion).
- Hemoglobin $<9 \text{ g/dL}$ or $<5.6 \text{ mmol/L}$ (without transfusions within 2 weeks of initiation of IMP).
- Total bilirubin $>2 \times \text{ULN}$.
- AST and/or ALT $>3 \times \text{ULN}$ (or $>5 \times \text{ULN}$ for participants with liver metastases).
- Blood creatinine $>1.5 \times \text{ULN}$ or creatinine clearance of $<50 \text{ mL/min}$ (using Cockcroft Gault formula or 24-hour urine collection)
- Prothrombin time (PT)/international normalized ratio (INR) and activated partial thromboplastin time or partial thromboplastin time (aPTT/PTT) $>1.3 \times \text{ULN}$ or outside the therapeutic range of the local laboratory if receiving therapeutic anticoagulation that would affect the PT/INR.

Other exclusions

E 24. Individuals accommodated in an institution because of regulatory or legal order; prisoners or participants who are legally institutionalized.

E 25. Participant not suitable for participation, whatever the reason, as judged by the Investigator, including medical or clinical conditions, or participants potentially at risk of noncompliance to study procedures.

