6.5.1 Prohibited concomitant therapy

In addition to prohibited medications/foods listed in Exclusion Criteria ([Section 5.2](#)), a complete list of prohibited medications during study treatment is provided in Appendix 10 ([Section 10.10](#)).

The following medications are prohibited while on study treatment:

- Medications known to prolong QTc interval
- Anti-cancer therapy (except SAR442720 and pembrolizumab or adagrasib)
- Strong CYP3A4 inhibitors and inducers
- Strong P-gp inhibitors
- Strong BCRP inhibitors (Part-3 only)
- CYP3A substrates with a narrow therapeutic index (Part-3 only)

- Proton pump inhibitors (only during the dose escalation portion of the study; for Part-3 during both escalation and expansion).
- H2-receptor antagonists (only during the dose escalation portion of the study). H2-receptor antagonist can be given at least 2 hours before and 10 hours after adagrasib (Part-3 only).
- Acetylsalicylic acid (low dose aspirin and anticoagulation with low-molecular weight heparin or direct Factor X inhibitors and LMWH are allowed. Prophylactic LMWH is also allowed for high risk patients with hypercoagulability).

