In Part-4, up to approximately 12 participants are expected to be enrolled. By assuming intra-subject variability of the steady-state AUC is [REDACTED], 12 participants will achieve a maximum imprecision of [REDACTED]. When 9 participants are PK evaluable, the maximum imprecision will be approximately [REDACTED].

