## 4.8 OTHER ANALYSES

### 4.8.1 PK analyses

Concentrations of SAR442720, pembrolizumab and adagrasib will be summarized by scheduled visit and nominal timepoint.

All concentration values below the lower limit of quantitation (LLOQ) will be treated as zero in all summary statistics excepted for the geometric mean and associated coefficient of variation for which they will be considered as missing.

For Part-3A and Part-4, PK parameter estimates, including but not limiting to the ones listed below, will be determined when possible, for SAR442720 and adagrasib:

- Maximal concentration: Cmax (observed)
- Time to reach maximal concentration: Tmax (observed)
- Area-under-the-curve from time 0 to t: AUC0-t
- Area-under-the-curve from time 0 to infinity, if possible: AUC0-inf, if possible
- t1/2, if possible
- Accumulation ratio

Unless otherwise specified, the PK parameters will be estimated based on noncompartmental analysis methods. These estimates will be summarized descriptively by dose cohort. All PK parameters will be computed using the actual elapsed time calculated relative to dose administration.

[figure not shown]
For Part-4, the geometric mean ratios and 90% confidence intervals of AUC0-inf and Cmax will be computed for SAR442720 between fed and fasted states of tablet formulation (C1D1 to C1D15) and between the tablet (test) and capsule (reference) formulations (C1D15 to C2D1). In addition, the PK parameters in Part-4 will be analyzed using a mixed effect model, which will be described in detail in the statistical analysis plan.

Population PK analysis may be conducted to obtain the PK parameters of SAR442720, pembrolizumab, and adagrasib. If performed, the results will be summarized in a separate report. Exploratory analyses may be performed to evaluate the relationship between the estimated PK parameters and PDs, selected safety, biomarker, or clinical effect endpoints.

The PK and PDy analyses will be presented in a separate report.

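### Part-4 has one PK-evaluable set that needs all three PK days, while each primary ratio uses only two, so a valid pair can be lost for an event on a day that its ratio does not use

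*SAP*

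**What the plan says.** SAP Table 3 gives Part-4 its own PK-evaluable population: "Patients who complete all of cycle 1 and C2D1 with meal information, full PK, and no dose reduction/missed doses on C1D1, C1D15 and C2D1". One relaxation follows in the same cell: "Missing some PK samples may still be considered as evaluable and will be assessed case-by-cased".

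SAP 4.8.1 plans geometric mean ratios with 90% confidence intervals for two comparisons. The food ratio is taken "between fed and fasted states of tablet formulation (C1D1 to C1D15") and the formulation ratio "between the tablet (test) and capsule (reference) formulations (C1D15 to C2D1"). It also plans a mixed effect model, and says that the SAP will describe it, but gives no description. The section does not say which population either ratio or the model uses.

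On size, Protocol 9.2 expects up to about 12 participants and adds: "When 9 participants are PK evaluable, the maximum imprecision will be approximately" a redacted value. SAP Section 2 makes the same 12 and 9 statement, also with its values redacted.

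On acid reducers, exclusion criterion E 22 names "Proton pump inhibitors (within 3 days prior) or H2-receptor antagonists (within 1 day prior) during the dose escalation portion of the study". Protocol 6.5.1 has "Proton pump inhibitors (only during the dose escalation portion of the study; for Part-3 during both escalation and expansion"), and limits H2 antagonists to dose escalation in the same way.

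**The concern.** The evaluability rule is stricter than either comparison needs. C2D1 is the capsule day and contributes nothing to the food ratio. C1D1 is the fed tablet day and contributes nothing to the formulation ratio. If the one set governs both ratios, each loses participants for an event on a day that it does not use. Both ratios are primary endpoints of Part-4, and both rest on about 9 to 12 participants, where every pair counts.

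**Working it through.** **1. Rule against ratios.**

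| Day | Treatment | Needed for food ratio | Needed for formulation ratio | Needed for PK-evaluable set |
|---|---|---|---|---|
| C1D1 | tablet, fed | yes | no | yes |
| C1D15 | tablet, fasted | yes | yes | yes |
| C2D1 | capsule, fasted | no | yes | yes |

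In Protocol Table 8 the last sample of the fed/fasted pair is the Day 16 sample, 24 hours after the Day 15 dose. C2D1 is nominally Day 22. A participant who stops between those days, or misses the C2D1 dose, has a complete food pair and fails the set. A missed C1D1 dose, or missing meal information, fails a participant who has a complete tablet/capsule pair. The relaxation covers missing samples only, so it rescues neither case.

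**2. Which set applies.** SAP 4.8.1 is silent. Two facts point to the PK-evaluable set: Table 3 limits it to Part-4, and the Part-4 precision statements are made for 9 PK-evaluable participants. The SAP gives it no other use.

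**3. Cost in precision.** The plan's own imprecision figures cannot be reproduced, because they and the assumed variability are redacted. I assume a paired log-scale 90% interval:

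half-width = t(0.95, n−1) × SD of the log-ratio / √n

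- n = 12: t(0.95, 11)/√12 = 0.518
- n = 9: t(0.95, 8)/√9 = 0.620
- ratio: 0.620/0.518 = 1.196, so 19.6% wider whatever the variability

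| n | half-width relative to n = 12 | widening from losing the last pair |
|---|---|---|
| 11 | 1.054 | 5.4% |
| 10 | 1.118 | 6.1% |
| 9 | 1.196 | 6.9% |
| 8 | 1.292 | 8.1% |
| 7 | 1.417 | 9.6% |

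For scale, take assumed within-participant CVs, with SD of the log-ratio = √(2 ln(1+CV²)). The upper limit then lies above the point estimate by:

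| Assumed CV | n = 12 | n = 9 |
|---|---|---|
| 20% | 15.6% | 19.0% |
| 30% | 24.0% | 29.3% |
| 40% | 32.6% | 40.2% |

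**4. Chance of reaching 9 food pairs from 12 enrolled.** Let q be the share with a complete fed/fasted pair, and r the share of those with a usable C2D1. Both are assumed, because the documents give neither. The count is binomial(12, qr) under the three-day rule and binomial(12, q) under a pairwise rule.

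| q = r | expected n, three-day | expected n, pairwise | P(n ≥ 9), three-day | P(n ≥ 9), pairwise |
|---|---|---|---|---|
| 0.95 | 10.8 | 11.4 | 97.6% | 99.8% |
| 0.90 | 9.7 | 10.8 | 82.0% | 97.4% |
| 0.85 | 8.7 | 10.2 | 56.3% | 90.8% |
| 0.80 | 7.7 | 9.6 | 32.0% | 79.5% |

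**5. Acid reducers.** E 22 and Protocol 6.5.1 tie the restriction to dose escalation (for proton pump inhibitors, also all of Part-3), and neither names Part-4. Protocol 6.5 has a general abstention clause covering prescription and nonprescription drugs, unless the investigator and sponsor judge that they will not interfere. Section 6.5.1 also presents Appendix 10 as the full prohibited list during treatment, and that appendix lists both classes without limit by part. These texts do not agree for Part-4.

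**The case against.** The best defence is that the documents never say that the three-day set governs the ratios. SAP Table 3 also defines a general PK population, which would keep this participant, and a mixed model could use all available profiles. This stands as a limit on certainty, but it does not remove the problem. Either the three-day set applies and pairs are lost, or two primary comparisons have no named population. The mixed model is too thinly described to settle which.

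A second defence is design intent. Protocol 4.2 wants both effects assessed in the same participants, calls the food assessment preliminary, and Protocol 9.1 states no formal hypothesis. That explains why the C1D15 profile is shared, and makes a common complete-case set defensible as a secondary view. It gives no reason to require the capsule day for a food ratio.

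Some loss routes that a reader might infer are narrower than they look:

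- Protocol 6.6 does not allow dose reduction on the three PK days, so the realistic routes at C2D1 are stopping or a missed dose.
- The rule asks for meal information, not adherence, so a recorded but imperfect breakfast does not fail it on its face.
- The gap between 12 and 9 is not a planned loss after C1D15. The amendment rationale simply describes a cohort of 9 evaluable participants.

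A reader might also infer that the food ratio becomes biased towards participants who tolerate the drug, because Protocol Table 11 gives median onsets of 15 days for thrombocytopenia, 17 for edema and 21.5 for anemia. The documents do not show this. Those medians are for onset, not for stopping or missing a dose. The any-grade events include uncomplicated Grade 1-2 thrombocytopenia, for which treatment continues. Diarrhea has a median onset of 9.0 days, before C1D15, where a resulting loss would spoil the food pair under either rule. In a within-participant ratio the exposure level largely cancels, and nothing links tolerability to the ratio itself.

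**Conclusion.** The concern holds as a mismatch between one evaluability rule and two comparisons. The cost is precision: about 5% to 10% of interval width per lost pair as n falls from 12 to 7, and 19.6% at n = 9 if all three losses come after C1D15. That last figure is an upper case. These relative figures assume a paired log-scale interval but no particular CV. The retention probabilities rest wholly on assumed q and r. That the three-day set applies is the likelier reading, but it is inferred.

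The documents do not support a claim of bias, nor a claim that acid reducers are permitted in Part-4 and distort the ratios. The rule has no concomitant-medication criterion, but the protocol's passages conflict on whether such drugs may be taken, and no document gives the size of any effect of acid reducers on SAR442720.

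**What to change.** In SAP Table 3, replace the single Part-4 set with two:

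- **Food-effect evaluable:** full-dose C1D1 and C1D15 profiles, with C1D1 meal information.
- **Formulation evaluable:** full-dose C1D15 and C2D1 profiles.

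In SAP 4.8.1, name the set for each ratio, and state that the planned mixed model uses every valid profile. The model has to be written out anyway, since the SAP refers to itself for the details.

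The cost is a few lines of SAP text and two population flags, with no new data. The one downside is that the two ratios may rest on slightly different participants. Keeping the common three-day set as a sensitivity analysis covers that.

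Separately, the sponsor should reconcile E 22, Protocol 6.5, Protocol 6.5.1 and Appendix 10 on acid reducers in Part-4. Which rule applies is for the sponsor to decide.
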